3.4 Primary Safety Endpoints

CONFIDENTIAL

Primary safety endpoints will consist of vital signs (blood pressure, pulse, oxygen saturation, and respiratory rate), measured every 15 minutes during the administration of ketamine and every 30 minutes in the ensuing 2 hours, and the Clinician-Administered Dissociative States Scale (CADSS) (Bremner et al., 1998).

4 Subject Selection and Withdrawal

4.1 Inclusion Criteria

Patients will be eligible to participate in the study if all of the following conditions exist:

- 1) Willing and able to provide informed consent and assent.
- 2) Male and female adolescents aged 12 to 18 years.
- 3) Presence of recurrent MDD confirmed by the K-SADS-PL (Kaufman et al., 1997).
- 4) Current depression severity measured by the Children's Depression Rating Scale (CDRS) (Poznanski, 1985) raw score greater than or equal to 36 at screening and the day ketamine is due to be received for the first time.
- 5) Current depressive episode resistant to treatment, defined as failure to achieve remission (elimination of symptoms and restoration of pre-morbid psychosocial functioning) from at least 2 antidepressant trials. Systematic evaluation of previous antidepressant trials will be assessed by using the Antidepressant Treatment History Form (Sackeim, 2001).
- 6) If present, current antidepressant medication treatment must be dose stable for at least 2 months prior to beginning the study*
- 7) Participants should have a medical history and physical examination in the 30 days prior to initiating the ketamine infusions.

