3.2 Primary Study Endpoints

The primary outcome measure is response status as defined by Children's Depression Rating Scale (CDRS) (Poznanski, 1985) Responders will be defined as having a significant reduction in their CDRS score ($\geq 50\%$) whereas non-responders will be defined as subjects whose scores do not show such a significant reduction or whose score increase. The percent change will be calculated by the formula below (Tao, 2009):

$$(\text{Baseline CDRS} - \text{Exit CDRS}) / (\text{Baseline CDRS} - 17)$$

Baseline CDRS: CDRS score obtained on Visit 1 – Baseline Assessment (Section 6.1)
Exit CDRS: the latest CDRS score obtained on Visit 10 - Clinical Assessment (Section 6.6) or Visit 11-16 – Follow-up Period (Section 6.7)

CONFIDENTIAL

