3.3 Secondary Study Endpoints

1. Montgomery-Åsberg Depression Rating Scale (MADRS) (Montgomery & Asberg, 1979) score of $\geq 50\%$. The MADRS has been used in most previous ketamine studies in adults and is designed to be sensitive to change. Although it has not been validated in adolescents, it has been used in several previous treatment studies of adolescent depression (Berard et al., 2006; von Knorring et al., 2006).
2. The Clinician-Administered Dissociative States Scale (CADSS) (Bremner et al., 1998)
3. The Profile of Mood States-Adolescent Version (POMS-A) (Terry et al., 1999)
4. The Beck Depression Inventory-II (Beck, 1988) which has been validated for adolescents (Osman et al., 2004)
5. The four-item positive symptom subscale of the Brief Psychiatric Rating Scale (BPRS) (Overall, 1962) consisting of suspiciousness, hallucinations, unusual thought content, and conceptual disorganization.
6. Relapse will be defined as a CDRS score $\geq 50\%$ of the pre-ketamine baseline. The onset of relapse will be calculated as the day halfway between the date of relapse and the previous date of response.
7. Biological endpoints will include MRI-based measures and blood-based measures of neuroplasticity.
8. The Clinical Global Impressions Scale (CGI) (Guy, 1976)

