6.3 Visit 3 – First ketamine infusion

On the day of each infusion, participants will arrive at the University of Minnesota Masonic Children's Hospital - Journey Clinic infusion center. Adolescent participants who are currently inpatient on the adolescent psychiatric ward will be escorted to the Journey clinic by hospital staff (four floors up the elevator). Adolescent participants who are outpatient will arrive at the Journey Clinic with their parent or guardian. An indwelling catheter will be placed in the non-dominant arm for ketamine administration and for two blood draws at the first infusion visit.

At this visit, directly before the ketamine infusion, participants will have 20 cc of blood drawn into heparinized tubes. They will have a second blood draw two hours after the infusion is complete. The blood samples will be sent to [name] at the Mayo Clinic for analysis.

Subjects will receive IV infusion of 0.5 mg/Kg of ketamine hydrochloride over 40 minutes. Digital pulse oximetry, respiratory rate, heart rate and blood pressure will be recorded every 15 minutes throughout the infusion, beginning 15 minutes before infusion. Vital signs will be monitored for at least 2 hours post infusion, to be assured there are no lingering side effects before leaving the unit.

Prior to infusion, participants will be asked to complete the BDI-II, SHAPS, TEPS and POMS-A, and a trained member of research staff will complete the Clinical Global Impressions Scale (CGI) (Guy, 1976), BPRS+, MADRS, CADSS. At the end of the infusion and 1 hour post infusion, participants will be asked to complete SHAPS, TEPS and POMS-A, and a trained member of research staff will complete BPRS+ and CADSS. At 2 hours post infusion, participants will be asked to complete the BDI-II, MADRS, SHAPS, TEPS and POMS-A, and a trained member of research staff will complete the Clinical Global Impressions Scale (CGI) (Guy, 1976), BPRS+, MADRS, CADSS.

If adolescent reports experiencing nausea or vomits during the infusion or the subsequent 2-hour observation period, the PI will evaluate the adolescent's reported symptoms and determine if (a) P.R.N. Ondansetron is indicated at that time (0.15mg/kg, up to 8mg), and (b) pre-treatment with IV Ondansetron for control of nausea is warranted for the subsequent infusions.

Participants will be asked about any adverse events (AE) and concomitant medications at each visit.

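### The CDRS score that criterion 4 requires on the first infusion day is missing from the Visit 3 assessments, and response is measured from Visit 1, so any fall before dosing counts toward ketamine response

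*Combined protocol and SAP*

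**What the plan says.** - **Eligibility (section 4.1, criterion 4).** The CDRS must be a "raw score greater than or equal to 36 at screening and the day ketamine is due to be received for the first time". Two scores are needed, the second on the day of the first infusion.
- **First infusion day (section 6.3, Visit 3).** "Prior to infusion, participants will be asked to complete the BDI-II, SHAPS, TEPS and POMS-A", and staff complete the CGI, BPRS+, MADRS and CADSS. The CDRS is not listed before or after the infusion. Section 6.4 carries the same list to the later infusions.
- **Response (section 3.2).** "The percent change will be calculated by the formula below": (Baseline CDRS − Exit CDRS) / (Baseline CDRS − 17), with response at 50% or more. The baseline is the "CDRS score obtained on Visit 1". The exit score is the latest from Visit 10 or Visits 11-16.
- **Other uses of a baseline.** Section 3.3 defines relapse by reference to 50% "of the pre-ketamine baseline", and the paired t test in section 7.3 uses baseline symptom levels. Neither names a visit.
- **Timing.** Section 6.8 puts the MRI row within a week of the first visit. No maximum interval from Visit 1 to the first infusion is given.
- **Design.** Single group, open label, 20 participants.

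**The concern.** The eligibility rule and the visit schedule do not match: section 4.1 needs a score that section 6.3 does not schedule. Taking the score anyway would not settle the matter, because section 3.2 still computes response from Visit 1.

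The primary outcome is response status. Whatever happens to the CDRS between Visit 1 and the first infusion lies inside Baseline minus Exit, and there is no comparator to remove it. A fall in that interval, from natural course, from expectancy on entering the study or from inpatient care (section 4.3 recruits inpatients), would be reported as response to ketamine. A rise would act the other way. Section 5.2 says that preliminary evidence of efficacy from this pilot is meant to lead to a randomized placebo-controlled trial, so an inflated response rate would carry into that decision.

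**Working it through.** The plan states no figure for change before dosing, and section 7.1 gives no inputs for the sample of 20, so there is nothing of the plan's own to reproduce.

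**1. Where the CDRS is scheduled.** Visit 1 (section 6.1), Visit 10 (6.6), Visits 11-16 (6.7) and the 6-month contact (4.4). Visit 1 is therefore the only listed CDRS before ketamine, and the unnamed baselines in 3.3 and 7.3 would default to it for this scale. MADRS and BDI-II appear at Visit 1 (6.1) and again before the first infusion (6.3).

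**2. The formula applied to the interval before dosing.** A participant at the floor of 36 on the infusion day is still eligible. Change already accrued is (B − 36)/(B − 17):
- B = 50: 14/33 = 42%
- B = 55: 19/38 = 50%
- B = 60: 24/43 = 56%
- B = 70: 34/53 = 64%

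A full response before any drug is thus arithmetically possible from a Visit 1 score of 55 upward.

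**3. Partial credit.** From a Visit 1 score of 60, response needs a drop of 0.5 × (60 − 17) = 21.5 points. A fall to 50 before dosing supplies 10/21.5 = 47% of it, and a fall to 45 supplies 15/21.5 = 70%. With scores of 60 at Visit 1, 48 on the infusion day and 38 at exit:
- Visit 1 baseline: (60 − 38)/(60 − 17) = 22/43 = 51%, a responder.
- Infusion-day baseline: (48 − 38)/(48 − 17) = 10/31 = 32%, a non-responder.

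**4. Size across a group.** All inputs here are assumptions: mean severity 50, 55 or 60; between-person SD 9; within-person SD 4, 6 or 8; a true 40% reduction above 17 after dosing; both pre-dose scores at least 36. Visit 1 score = true severity + error. Infusion-day score = true severity − fall + error. Exit score = 17 + 0.6 × (true severity − fall − 17) + error.

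| Assumed mean fall before dosing | Response, Visit 1 baseline | Response, infusion-day baseline | Inflation within a setting | Already at 50% before dosing |
|---|---|---|---|---|
| 0 points | 17-37% | 17-37% | 0 points | under 1% |
| 2 points | 25-41% | 18-38% | about 4-7 points | up to 1.3% |
| 5 points | 38-49% | 20-40% | about 9-19 points | up to 2.3% |

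Rounding scores to whole points leaves the inflation essentially unchanged and moves the last entry to 2.8%. In a group of 20, 4-7 points is 0.8 to 1.4 participants and 9-19 points is 1.8 to 3.8.

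**5. A second set of assumptions** (mean 55, between-person SD 10, error SD 6, floor on both days). Expected responders out of 20, Visit 1 versus infusion-day baseline:
- No fall: 2.8 versus 2.8 (30% true effect); 6.0 versus 6.0 (40%).
- 5-point fall: 5.5 versus 3.5 (30%); 9.2 versus 6.6 (40%).
- 10-point fall: 8.9 versus 4.3 (30%); 12.5 versus 7.3 (40%).

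**The case against.** - **The criterion can be checked.** A reader might infer that criterion 4 cannot be verified as written. The documents do not support that. Criterion 4 is itself an instruction to obtain the score, and section 3.1 says symptoms are assessed before infusion without naming a scale. What stands is narrower: the visit list omits an assessment that eligibility requires. The table in 6.8 adds little, since it also leaves out questionnaires that 6.3 does schedule on infusion days.
- **Change before dosing is partly visible already.** MADRS and BDI-II are taken at both visits, so drift can be described on two depression scales. This stands, but neither scale adjusts the CDRS response formula.
- **Drift may be small.** Participants have failed to remit with at least 2 antidepressant trials, any current antidepressant must have been dose stable for 2 months, and the MRI falls within a week of Visit 1. This argues for a modest change. It does not exclude one, because the interval to the first infusion is not capped.
- **The stated primary analysis is a paired t test, and section 7.3 names no baseline visit.** That is correct. The inflation above concerns the responder endpoint of section 3.2. The t test shares the problem only if Visit 1 is used there, which is the default because no other CDRS before ketamine is listed.
- **A new baseline does not make the study controlled.** Also correct. Expectancy and natural course after dosing remain in the estimate.

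**Conclusion.** The mismatch between sections 4.1 and 6.3 is certain on the text, and so is the Visit 1 baseline in 3.2. The bias is conditional: it depends on the mean CDRS change between Visit 1 and the first infusion, which the documents do not give and which the plan, as scheduled, would not record on its primary scale. Under the stated assumptions the inflation is nil with no mean fall, about 4-7 points with a 2-point fall and about 9-19 points with a 5-point fall.

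The step from 55 to 36 might lead a reader to infer that many participants would be responders before any drug. The documents do not show that, and under these assumptions it occurs in about 2% of eligible participants at most (nearer 3% with whole-point scores). The main route is partial credit toward the 50% threshold. Nor do the documents show that a fall before dosing will occur. The point should be corrected because the repair is cheap and touches the primary outcome, not because a given amount of inflation has been shown.

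**What to change.** 1. In section 6.3, add the CDRS-R to the assessments before the first infusion, and mark it in the first-infusion row of section 6.8.
2. In section 3.2, define Baseline CDRS as that score. Name the same score as the relapse baseline in 3.3 and as the CDRS baseline for the paired t test in 7.3. Keep Visit 1 for screening.
3. Report response from the Visit 1 baseline as a sensitivity analysis.
4. Describe the change from Visit 1 to Visit 3 on the CDRS, MADRS and BDI-II.

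The cost is protocol wording and one interview that criterion 4 already requires. There are three small downsides. The reported response rate may be slightly less favourable. The Visit 3 score is itself thresholded at 36, so some selection on that score remains. The CDRS-R uses separate adolescent and parent interviews, so both must be arranged for that day, including for inpatients whom hospital staff escort to the infusion. No eligibility threshold or treatment rule changes.

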4.2 Exclusion Criteria

Patients will be excluded from participation in the study if any of the following conditions exist:

1. Inability to speak English
2. A history of Mental Retardation or Autism Spectrum Disorder
3. Current or lifetime diagnosis of schizophrenia, schizoaffective disorder, psychosis not otherwise specified (NOS).
4. Diagnosis of seizures or other neurological disorders.
5. Comorbid diagnosis of substance abuse or dependence within 6 months of assessment.

CONFIDENTIAL

6. Clinically unstable medical illness.
7. Current use of barbiturates, narcotics, or non-benzodiazepine hypnotics at doses higher than Zolpidem 10 mg or equivalent for insomnia.
8. For females: pregnancy.
9. Inability to undergo an MRI scan.
10. A Family History notable for having at least one first-degree relative with schizophrenia, schizoaffective disorder, psychosis not otherwise specified (NOS).

* If there has been a recent discontinuation of a medication, we will require lapses of time before study entry as follows: Antidepressants (excluding Fluoxetine) – 2 weeks; Fluoxetine – 4 weeks; Mood Stabilizers – 2 weeks; Antipsychotics – 2 weeks; Stimulants – 1 week.

4.3 Subject Recruitment and Screening

Adolescents with treatment resistant depression who have been admitted to the adolescent mental health inpatient unit, who present to the University of Minnesota Psychiatry Adolescent Mood Clinic, or who are referred from outside clinicians, and who meet inclusion and exclusion criteria for the study, will be invited to participate.

Prior to enrollment, project staff selected to recruit for this study will screen review records from the hospital and clinical services noted above to determine potentially eligible adolescent participants. If an adolescent appears to meet basic criteria for the study (appropriate age and diagnosis), staff will then check the consent for treatment form in the patient's chart. If parents indicated on that form their willingness to have their child's medical records used in research, study staff will then contact the current treating provider to determine whether the provider feels it would be appropriate to invite this participant into the study. If so, the provider will request written permission of the adolescent and/or the parent for the study staff to contact them regarding the study. The study staff will then contact the parents by phone or in person to inform them about the purpose and activities of the current study.

We anticipate that some families will hear about our study through word of mouth or by searching on ClinicalTrials.gov. We will post information about the study in the community using flyers and online posting boards.

If after hearing about the study from study staff patients/families are interested in participating, the study staff will then conduct a screening form to ensure eligibility. If parents are interested and the adolescent is eligible, the first study visit will be scheduled. Informed consent will be obtained at the time of the first study visit.

CONFIDENTIAL

4.4 Early Withdrawal of Subjects

When and How to Withdraw Subjects

A subject may be withdrawn from the study prior to expected completion for the following reasons:

- Participant experiences adverse side effects to the ketamine treatments that are intolerable to the adolescent or the parent.
- Participant fails to adhere to protocol requirements
- Participant or participant's parent(s) withdraw consent

If a subject exits the study for any reason (withdrawal, non-response, or relapse), he or she will continue his or her pre-study regimens and consult with his or her psychiatrist about the next step in treatment.

Data Collection and Follow-up for Withdrawn Subjects

For all participants, we will request permission during the consent process to collect naturalistic follow-up data through in person visit to clinic or video conference 6 months after the 6-week study period.

The naturalistic follow-up encounter will be as follows:

We will ask permission to contact the family to inquire about the participant. Subjects will be determined lost to follow-up if they do not respond to 4 e-mails to the primary e-mail address of parent(s) or 4 phone calls to their primary number or to their next-of-kin, or to a certified letter.

During the follow up in person visit to clinic or video conference subject will be asked to provide:

- a) A narrative interval history including following elements
 - a. Changes in medications and their effects
 - b. Therapies or other treatments they have undergone and their effects
 - c. Evolution of their symptoms during the interval
 - d. Any hospitalizations including cause and outcome
 - e. Any suicide attempts including precipitating factor (if any) and outcome
- b) Participate in a clinical interview in order for clinician to complete an assessment using CDRS-R, CADSS, CGI, and MADRS.
- c) Complete the BDI-II, Profile of Mood States – Adolescent, SHAPS and TEPS

5 Study Drug

5.1 Description

Study solutions of ketamine will be prepared as a liquid in 50mL IV bag, with 0.9% saline and a dose of ketamine that equal 0.5mg/kg of the subject's actual body weight, dissolved into the saline.

CONFIDENTIAL

This material is the property of the University of Minnesota. Do not disclose or use except as authorized in writing by the study sponsor

5.2 Treatment Regimen

At each of the ketamine treatment visits, subjects will receive an IV infusion of 0.5mg/Kg of ketamine hydrochloride over 40 minutes. To ease IV placement, we will use emla cream, or if necessary, J tip (a needle-free injector that uses compressed air to propel lidocaine beneath the skin's surface, numbing the area). The dose of ketamine will be determined by body weight.

Each participant will undergo a total of 6 ketamine infusions over a 2-week period (on a Monday, Wednesday, Friday schedule).

For this pilot study we do not include a placebo in the design. After confirming the feasibility of recruiting adolescents with TRD to a ketamine study and showing preliminary evidence of efficacy and mechanism, a future step will be to conduct a randomized placebo controlled trial.

Patients will continue with current antidepressant treatment throughout the study. Based on our experience in current research at the VA Medical Center using serial ketamine dosing, patients have shown positive results while continuing their current antidepressant treatment.

5.3 Method for Assigning Subjects to Treatment Groups

Not applicable. There is only one treatment group.

5.4 Preparation and Administration of Study Drug

The IV ketamine study medication will be prepared in the Investigational Pharmacy and administered by the nursing staff in the Journey Clinic.

5.5 Subject Compliance Monitoring

Since the study medication is administered in an infusion unit, compliance with study medication will be measured by whether participants present to infusion visits and cooperate with all procedures of IV ketamine administration. To be compliant with other aspects of the study, participants will be required to attend two MRI scans, six ketamine treatment visits and six weekly follow-up visits. The follow up visits may take place in person or, for subjects who do not reside within convenient travel distance to Minneapolis, via phone or video conference. Study staff will monitor whether the participant is attending these visits. If a participant is not compliant with study procedures, his/her participation in the study will be terminated.

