6.7 Visits 11-16 – Follow-up period

All participants will be asked to speak with the research team for weekly follow-up visits for 6 weeks. Participants will continue to take medications as prescribed by their doctor. At each of these visits, participants will be asked about any medication changes and will complete the same assessments as administered in visit 10 (MADRS, CADSS, POMS-A, SHAPS, TEPS, BDI-II, CGI, CDRS and BPRS).

All participants will be asked to participate in the 6 weekly follow-up visits, regardless of response.

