8.1 Definitions

Adverse Event

An **adverse event** (AE) is any symptom, sign, illness or experience that develops or worsens in severity during the course of the study. Intercurrent illnesses or injuries will be regarded as adverse events. Abnormal results of diagnostic procedures are considered to be adverse events if the abnormality:

- results in study withdrawal
- is associated with a serious adverse event
- is associated with clinical signs or symptoms
- leads to additional treatment or to further diagnostic tests
- is considered by the investigator to be of clinical significance

Serious Adverse Event

Adverse events are classified as serious or non-serious. A **serious adverse event** is any AE that is:

- fatal
- life-threatening
- requires or prolongs a hospital stay
- results in persistent or significant disability or incapacity
- a congenital anomaly or birth defect
- an important medical event

Important medical events are those that may not be immediately life threatening, but are clearly of major clinical significance. They may jeopardize the subject, and may require intervention to prevent one of the other serious outcomes noted above. For example, drug overdose or abuse, a seizure that did not result in in-

CONFIDENTIAL

patient hospitalization, or intensive treatment of bronchospasm in an emergency department would typically be considered serious.

All adverse events that do not meet any of the criteria for serious should be regarded as *non-serious adverse events*.

Adverse Event Reporting Period

The study period during which adverse events must be reported is normally defined as the period from the initiation of any study procedures to the end of the study treatment follow-up. For this study, the study treatment follow-up is defined as 30 days following the last administration of study treatment.

Preexisting Condition

A preexisting condition is one that is present at the start of the study. A preexisting condition will be recorded as an adverse event if the frequency, intensity, or the character of the condition worsens during the study period.

General Physical Examination Findings

At screening, any clinically significant abnormality will be recorded as a preexisting condition. At the end of the study, any new clinically significant findings/abnormalities that meet the definition of an adverse event will also be recorded and documented as an adverse event.

Post-Study Adverse Event

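### Sections 4.4 and 5.5 do not separate stopping infusions from leaving the study, so a dosed participant who leaves in the infusion phase has no scheduled contact in the 30-day adverse event window and no exit CDRS

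*Combined protocol and SAP*

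**What the plan says.** Section 5.5 defines compliance by attendance: "participants will be required to attend two MRI scans, six ketamine treatment visits and six weekly follow-up visits". The consequence is mandatory and reaches beyond treatment: "If a participant is not compliant with study procedures, his/her participation in the study will be terminated".

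Section 4.4 is permissive: "A subject may be withdrawn from the study prior to expected completion for the following reasons". Three reasons follow: intolerable effects ("Participant experiences adverse side effects to the ketamine treatments that are intolerable to the adolescent or the parent"), failure to adhere to the protocol, and withdrawn consent. After exit, the subject returns to the prior regimen and his or her own psychiatrist: "If a subject exits the study for any reason (withdrawal, non-response, or relapse), he or she will continue his or her pre-study regimens". Under its heading on data collection for withdrawn subjects, 4.4 offers a single item, which is requested of all participants and needs permission: to "collect naturalistic follow-up data through in person visit to clinic or video conference 6 months after the 6-week study period".

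Other sections bear on the same participants:

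- Section 6.7: "All participants will be asked to participate in the 6 weekly follow-up visits, regardless of response". It does not mention withdrawal or stopped infusions.
- Section 8.1, on the adverse event reporting period: "For this study, the study treatment follow-up is defined as 30 days following the last administration of study treatment".
- Sections 8.1 and 8.2: unresolved events are followed. Subjects are told at the last scheduled visit to report later events that may be related. Possibly related serious events after the study period are reported.
- Section 7.2: the primary analysis uses those who complete six infusions, and secondary analyses use everyone with at least one dose.

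Sections 6.1 to 6.8 contain no early-termination visit.

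**The concern.** Stopping the drug and ceasing to be observed are different events, and the plan treats them as one. If 5.5 is applied as written, observation ends when attendance fails. If 4.4 is applied as written, it can end because of side effects. Intolerability is a listed reason for leaving, so the loss is unlikely to be random with respect to harm. Later adverse events and durability data would be missing selectively, and the safety profile after the infusion day could look better than it is.

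There is also an analysis cost. The plan promises results on everyone dosed at least once, but for someone who leaves before Visit 10 it schedules no measurement from which the response endpoint could be computed.

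**Working it through.** The plan states no gap, dropout rate or power figure for this point, so there is nothing to reproduce. The check has three parts.

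**1. Length of the gap**

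Inputs: six infusions on a Monday-Wednesday-Friday pattern that may start on any of those days (5.2, 6.8), so the sixth falls on day 11 or 12 with the first on day 0. The contact is 6 months after the 6-week study period (4.4). The end of that period is unclear: 3.1 gives both a 4-week post-treatment period and weekly assessment for 6 weeks after the last infusion. Four readings are therefore used. One month is taken as 30.4375 days, so 6 months is 182.6 days.

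Gap in months = (E + 182.6 − L) / 30.4375, where E is the day the study period ends and L is the day of the last attended visit.

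| Reading of study period end | E (day) | 6-month contact (day) | Gap, leaving after infusion 1 | Gap, leaving after infusion 6 |
|---|---|---|---|---|
| 6 weeks from first infusion | 42 | 224.6 | 7.38 | 6.99–7.02 |
| 8 weeks from first infusion | 56 | 238.6 | 7.84 | 7.45–7.48 |
| 6 weeks after last infusion | 53–54 | 235.6–236.6 | 7.74–7.77 | 7.38 |
| Visit 10 at +7 days, then 6 weeks | 60–61 | 242.6–243.6 | 7.97–8.00 | 7.61 |

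Example: (42 + 182.6 − 0) / 30.4375 = 7.38. Leaving during the infusion phase gives 7.0 to 8.0 months.

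For someone who leaves after follow-up week 1, the gap is 6.76 to 7.38 months. After week 5 it is 5.84 to 6.46 months. The lowest values come from the first reading, under which week 5 (day 46 or 47) already lies beyond day 42. Without that reading the week-5 minimum is 6.23. About 6 to 7 months is a fair summary.

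**2. Contacts inside the 30-day window**

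The window closes on day 30 for someone who stops after infusion 1 and on day 41 or 42 after infusion 6. A completer has Visit 10 (within a week of the last infusion) plus weekly contacts at 7, 14, 21 and 28 days, or at 14, 21 and 28 if the weeks run from a Visit 10 held at 7 days. That is four or five contacts. A participant withdrawn or terminated during the infusion phase has none scheduled. Adverse events are elicited at visits and contacts (6.3, 8.2), so without a contact nothing prompts the question.

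**3. Measurements available for someone who leaves before Visit 10**

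- CDRS: done at Visit 1. Section 4.1 also requires a qualifying score on the first infusion day, which is an eligibility value. It is not in the infusion-visit list of 6.3. Section 3.2 takes the exit score only from Visit 10 or Visits 11–16. Result: no exit CDRS and so no response status.
- C-SSRS: done at Visit 1 and next listed at Visit 10. It is absent from 6.3. The 6-month contact asks about suicide attempts but does not list the scale. Result: no scheduled post-dose C-SSRS.
- MADRS, BDI-II, CADSS and vital signs: collected at each infusion visit, so available for the doses received.

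**Number affected.** On an assumed early-exit rate of 10 to 25%: 0.10 × 20 = 2 and 0.25 × 20 = 5.

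**The case against.** The best defence is that the plan is looser than the gap suggests. Section 6.7 asks all participants to attend weekly follow-up and could include those who stopped infusions. Adverse event duties do not lapse at exit: the 30-day window has no exception for early leavers, unresolved events are followed, and some new events are reached by subject report. The primary safety endpoints in 3.4 (vital signs and CADSS) are captured on the infusion day, before anyone leaves. The primary analysis uses completers of six infusions, so those who leave during dosing do not enter it. This is a 20-person pilot.

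Much of that stands, and it rules out several stronger readings that a reader might infer:

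- *One missed visit ends participation.* Section 5.5 sets no threshold for non-compliance, and 4.4 makes withdrawal discretionary.
- *Non-responders and relapsers are removed.* Neither is among the three listed reasons in 4.4. They appear only in a parenthesis about the regimen after exit, while 6.7 keeps everyone regardless of response and 7.3 computes time to relapse for each participant.
- *A waived MRI breaches compliance.* Section 6.2 grants the waiver itself.
- *Early leavers have no safety follow-up.* They have no scheduled contact, which is narrower. The instruction to report later events is tied to the last scheduled visit, which an early leaver may not attend.
- *Every leaver waits 7 to 8 months.* That holds only for the infusion phase.

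What the defence does not supply is any section that schedules a contact for a withdrawn or terminated participant before the 6-month one. Section 6.7 is silent on withdrawal, so it leaves the conflict with 5.5 unsettled.

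**Conclusion.** The point holds in limited form. For a dosed participant who leaves during the infusion phase, the plan schedules no contact for about 7 to 8 months, none in the 30-day adverse event window, no exit CDRS and no post-dose C-SSRS. For one who leaves during weekly follow-up, the gap is about 6 to 7 months. The at-least-one-dose analyses in 7.2 cannot use the CDRS response endpoint for those who leave before Visit 10, although scales taken at infusion visits remain usable.

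This rests on applying 4.4 and 5.5 as written and on the last attended visit being the last contact. The number affected is unknown because no dropout rate is given; 2 to 5 of 20 is illustrative. This is a cheap improvement worth making. It does not undermine the design.

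**What to change.** Amend 4.4 and 5.5 so that a participant who has received at least one infusion and then stops infusions or misses procedures stays in the study for data collection unless consent is withdrawn. That participant has Visit 10 and the six weekly contacts, with adverse events collected, timed from the last infusion received. Phone or video is already allowed. This concerns observation only and changes no rule on treatment.

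In the same amendment:

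- Reconcile the discretionary withdrawal in 4.4 and its parenthesis on non-response and relapse with the mandatory termination in 5.5 and the follow-up of all participants in 6.7.
- State that an MRI waived under 6.2 is not non-compliance.
- Name the contacts that cover the 30-day window in 8.1 for early leavers.
- Settle the 4-week and 6-week periods in 3.1 against the study period in 4.4, since they date the 6-month contact.

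The cost is a protocol amendment and a few remote contacts per early leaver, with existing forms and staff. Under 11.3 the payments are $10 per weekly visit and $20 for the clinical assessment after six infusions, so at most 6 × $10 + $20 = $80 per early leaver if the $20 is also paid for a Visit 10 held early.
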